3.2 Rationale for Study Design and Dose Selection

The current MTI-107 study is designed to confirm the long-term safety of seriopitant for the treatment of pruritus in patients with PN, AD, and psoriasis. The 5 mg dose of seriopitant was selected for this study based on the favorable efficacy, safety, and tolerability profile of seriopitant at this dose level in completed studies.

3.3 Study Endpoints

3.3.1 Safety Endpoints

The safety endpoints are as follows:

- Incidence of TEAEs and SAEs
- Changes from baseline in clinical laboratory parameters following study drug exposure
- Changes from baseline in vital sign and ECG parameters following study drug exposure
- Assessment of physical dependence following chronic study drug exposure, in the 4-week post-drug discontinuation period.

3.3.2 *Efficacy Endpoints*

The efficacy endpoints are as follows:

- Changes from baseline in WI-NRS to Weeks 4, 8, 20, 28, 36, 44, and 52
- Changes from baseline in PROMIS-PIQ score for Itch (General, Scratching Behavior, Mood and Sleep, Activity and Clothing) to Weeks 20, 36, and 52

- Changes from baseline in DLQI (symptoms and feelings, daily activities, leisure, work or school performance, personal relationships, and treatment) to Weeks 20, 36 and 52
- Changes from baseline in IGA PN-S to Weeks 4, 8, 20, 28, 36, 44, and 52

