The results of the Phase 2 studies in PN and chronic pruritus, together with the extensive nonclinical and clinical safety data and experience with serlopitant to date and the scientific rationale for NK₁-R inhibition in the treatment of pruritus, serve to support further evaluation of serlopitant for the long-term treatment of pruritus in patients with PN, AD, or psoriasis. The potential benefits of continued clinical study outweigh the potential risks. The data obtained from this long-term study will inform the risks and benefits of long-term exposure (chronic or repeated intermittent use for longer than 6 months). The risk to subjects in this study will be minimized by medical and safety monitoring (see Section 3.4.1).

Please refer to the Investigator's Brochure for further information regarding seriopitant.

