3 STUDY DESIGN

3.1 Overall Study Design

This is a multicenter, open-label study to assess the long-term safety of seriopitant in adults with pruritus associated with PN, AD, or psoriasis. Eligible subjects who have completed selected studies of seriopitant may be given the opportunity, at the investigator's discretion, to consent to and participate in this open-label study, regardless of their treatment allocation in prior studies. If deemed necessary by Menlo Therapeutics to meet enrollment objectives, eligible subjects who have not participated in a prior seriopitant study may also be enrolled in study MTI-107. Approximately 120 study sites may enroll subjects in this long-term safety study.

This study will consist of two periods, for a total study period of approximately 57 weeks:

- Treatment period: 52 weeks
- Post-drug observation period: 5 weeks

During the treatment period, subjects will take one seriopitant 5 mg tablet once daily orally (Section 5.3).

Standard therapy for the concurrent skin lesions and pruritus may be employed during this study (Section 5.7.1).

The WI-NRS during a 24-hour recall period will be assessed by the subject at each study visit.

For those subjects with PN, the severity and extent of PN will be assessed at selected visits, using the IGA-PN-S, and photographs of representative areas with PN will be taken at selected visits at a subset of sites.

The Dermatology Life Quality Index (DLQI) will be administered at selected visits.

After completion of the 52-week treatment period, all subjects will enter a 5-week post-drug observation period. Subjects who discontinue treatment early will have a post-drug observation visit through 5 weeks after their last dose of serlopitant. During this monitored discontinuation period, solicited safety evaluations will assess the potential for serlopitant to produce physical dependence.

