3.3 Study Endpoints

3.3.1 Safety Endpoints

The safety endpoints are as follows:

- Incidence of TEAEs and SAEs
- Change from baseline in clinical laboratory parameters
- Change from baseline in vital sign and ECG parameters
- Change from baseline in the Hospital Anxiety and Depression Scale (HADS)
- Change from baseline in the Epworth Sleepiness Scale (ESS)
- Assessment of physical dependence following chronic study drug exposure, in the 5-week post-drug discontinuation period.

3.3.2 *Efficacy Endpoints*

The efficacy endpoints are as follows:

- Change from baseline in WI-NRS to Weeks 4, 8, 20, 28, 36, 44, and 52
- Change from baseline in DLQI (symptoms and feelings, daily activities, leisure, work or school performance, personal relationships, and treatment) to Weeks 20, 36 and 52
- Change from baseline in IGA PN-S to Weeks 4, 8, 20, 28, 36, 44, and 52

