#### 2. INTRODUCTION

The MTI-107 study described herein is an open-label study to assess the long-term safety of serlopitant in adults with pruritus associated with prurigo nodularis (PN), atopic dermatitis (AD), or psoriasis.

Subjects enrolled in MTI-107 may have or may not have participated in previous Menlo Therapeutics Inc. studies. Previous study participation includes studies in PN (MTI-105, MTI-106, TCP-102), in AD (MTI-103) and in psoriasis (MTI-109).

The MTI-107 study has been terminated early by Sponsor. The Statistical Analysis Plan has been updated to facilitate an abbreviated clinical study report.

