# 5.2 Safety Endpoints

Safety endpoints include the following:

- Incidence of treatment-emergent adverse events (TEAEs) and serious adverse events (SAEs)
- Changes from baseline in clinical laboratory parameters
- Changes from baseline in vital sign and electrocardiogram (ECG) parameters
- Change from baseline in the Hospital Anxiety and Depression Scale (HADS)
- Change from baseline in the Epworth Sleepiness Scale (ESS)
- Assessment of physical dependence following chronic study drug exposure, in the monitored 5-week post-drug discontinuation period

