# 6.4 Data Sets Analyzed

# 6.4.1 Safety Population

All subjects who receive at least 1 confirmed dose of study drug and have at least 1 post-baseline safety assessment or a reported TEAE will be included in the safety population. All analyses will be performed using the safety population.

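### The dependence endpoint concerns chronic exposure, but SAP version 4 plans no output that isolates post-drug events or scores after chronic exposure

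*Protocol*

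**What the plan says.** **Objective and endpoint.** Protocol section 2 and SAP section 3 keep physical dependence as a secondary objective. The current endpoint in Protocol 3.3.1 (version 3.0) is "Assessment of physical dependence following chronic study drug exposure, in the 5-week post-drug discontinuation period". SAP 5.2 has "Assessment of physical dependence following chronic study drug exposure, in the monitored 5-week post-drug discontinuation period". The superseded version 1.0 differs only in the length of the period: "Assessment of physical dependence following chronic study drug exposure, in the 4-week post-drug discontinuation period". None of these sets a minimum time on drug. The nearest gloss on 'chronic' is background text in Protocol 1.2.3: "long-term exposure (chronic or repeated intermittent use for longer than 6 months".

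**Who is followed.** Protocol 3.1 says: "Subjects who discontinue treatment early will have a post-drug observation visit through 5 weeks after their last dose of serlopitant". Protocol 5.6 sends all early stoppers into a 5-week follow-up, however briefly they were treated. Protocol 6.2.7 has all TEAEs in the post-drug period medically reviewed for signs of dependence or withdrawal.

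**What is analysed.** SAP section 2 records that "The MTI-107 study has been terminated early by Sponsor". SAP 6.4.1 admits anyone with one confirmed dose plus a later safety assessment or a TEAE, and adds: "All analyses will be performed using the safety population". SAP 6.1.8 rules out subgroup summaries. SAP 6.8.2 tabulates TEAEs for the study as a whole. SAP 6.8.4.5 and 6.8.4.6 give HADS and ESS as by-subject listings. SAP 6.8.1 defines exposure flags at 182 and 358 days, which appear only in Table 14.3.0.1. The weekly post-drug TEAE tables of Protocol 8.8.1 are not in SAP version 4.

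**The concern.** The endpoint names a population (subjects stopping after chronic use) and a period (the five weeks after stopping). The planned outputs isolate neither. A withdrawal-type event after a year on drug goes into the same TEAE table as an event in the first week of dosing. A subject who stopped after days has the same weight as one who completed 52 weeks.

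At stake is whether the report can say anything specific on a stated objective. Early termination makes this more pressing, because some subjects will have stopped well before six months for reasons unrelated to the endpoint. The data for a matching summary are already being collected.

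**Working it through.** **1. The plan's own figures.** The dependence endpoint has no sample size, effect size or test to reproduce. The exposure cut-offs do reproduce: 26 × 7 = 182 days, and 364 − 7 + 1 = 358 days.

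**2. The flag as written.** SAP 6.8.1 and the footnote to Table 14.3.0.1 compute exposure as first-dose date minus last-dose date plus 1. For a subject dosed on 365 consecutive days this is −364 + 1 = −363. With the dates in the other order it is 364 + 1 = 365. Taken literally, no subject reaches 182 days.

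**3. Can a post-drug signal be seen in the tables?** The note to Table 14.3.1.3.1.1 defines a TEAE by onset after first dose, with no end point, so post-drug events are counted. For a completer the post-drug period is 5 of 57 weeks, or about 9% of observation. SAP 6.8.2 counts a subject once per preferred term, so an event that occurs on treatment and recurs after stopping adds nothing. The table index in SAP section 9 has no post-drug table.

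**4. Can it be seen in the listings?** The TEAE listing (16.2.7.1.2) shows first-dose date but not last-dose date. The HADS and ESS listings (16.2.7.2.1 and 16.2.7.2.2) number days from first dose and show neither last dose nor exposure. To tell whether a record is post-drug, and after how long on treatment, a reader must merge each one with the disposition listing (16.2.1.1).

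**5. What pooling could do.** This would apply to a pooled post-drug table, such as those in Protocol 8.8.1, and every input is an assumption. Let f be the share of stoppers with at least 182 days on drug, and let p_c and p_s be the post-drug event risks after long and short exposure:

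pooled risk = f × p_c + (1 − f) × p_s

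With p_c = 10% and p_s = 2%:

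| f | Pooled risk | Excess over 2% | Share of the 8-point excess kept |
|---|---|---|---|
| 0.90 | 9.2% | 7.2 points | 90% |
| 0.75 | 8.0% | 6.0 points | 75% |
| 0.50 | 6.0% | 4.0 points | 50% |
| 0.25 | 4.0% | 2.0 points | 25% |

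The share kept is f itself. Now swap the two risks, as could happen if early stoppers left because they were unwell. At f = 0.50 the pooled risk is 0.50 × 2% + 0.50 × 10% = 6.0%, three times the 2% in the longer-exposed group. Pooling can mislead in either direction, and the documents supply none of f, p_c or p_s.

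**6. Who has post-drug scores?** Protocol 6.4.11 times six visits, at 3 to 35 days, from the Week 52 Visit. Protocol 6.4.10 gives early discontinuers one visit within 35 days of last dose. Protocol 6.2.7 times HADS and ESS from the last dose, at days 3 and 7 and then weekly. The synopsis and Protocol 3.1 describe post-drug observation of early stoppers through 5 weeks. These passages do not agree.

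**The case against.** A reader might infer that short-exposure subjects dilute the withdrawal effect and push the result towards no dependence. The documents do not support that. SAP version 4 produces no pooled post-drug estimate, so there is no average to dilute: HADS and ESS are listings, and the medical review in Protocol 6.2.7 works case by case. The exposure distribution is not given. On the Protocol 6.4.11 schedule, post-drug scores would come mainly from completers. Early stoppers may include those who left for an adverse event or lack of efficacy, both of which are stopping reasons in Table 14.0.1.1, so their post-drug event rate could be raised.

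Other objections also have weight. The six-month phrase is background text, so applying 182 days to this endpoint is a choice and not a definition in the plan. The flag counts only dosing in this study. Subjects may roll over from parent studies regardless of their allocation there, so short exposure here need not mean short exposure in total. The abbreviation of the analyses is disclosed in SAP sections 2 and 8, and the study is descriptive throughout.

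All of this stands, and it limits the claim. It does not remove the mismatch: the objective and endpoint were kept, and no output corresponds to them. The listings hold the raw material, but only after a merge that the plan does not specify.

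**Conclusion.** The point holds in a limited form. The endpoint is about dependence after chronic exposure. SAP version 4 neither says what counts as chronic nor isolates post-drug events or scores in subjects so exposed. No planned output therefore answers a retained secondary objective for the population it names.

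The effect on any conclusion cannot be sized from the documents. The mixture figures show only the mechanism, under assumed risks and shares, and they run both ways. The one firm number is the flag error, −363 where 365 is meant. The change is worth making because the data exist and the work is small. No planned estimate is shown to be biased.

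**What to change.** 1. In SAP 6.8.1 and the footnote to Table 14.3.0.1, compute exposure as date of last dose minus date of first dose plus 1.
2. In SAP 5.2, 6.8.2, 6.8.4.5 and 6.8.4.6, with a matching exception in 6.1.8, add one descriptive post-drug summary of TEAEs with onset after last dose, HADS and ESS, timed from last dose. Show three columns: at least 182 days on drug, under 182 days, and all subjects. State that 182 days is the working meaning of chronic, and base the dependence statement on that set.
3. Label the under-182-day column a descriptive reference and not a control, because visit schedules and stopping reasons differ. Show parent-study serlopitant exposure where it is known.
4. Reconcile the passages on post-drug visits for early discontinuers: the synopsis and Protocol 3.1 and 6.2.7 against 6.4.10 and 6.4.11. Report how many subjects contribute at each post-drug time.

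**Cost.** One extra table in an abbreviated report, some SAP wording, and a smaller main set with wider uncertainty. The all-subject column keeps the full data in view.

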3.4 Safety Review

3.4.1 Safety Monitoring Team

An internal safety monitoring team consisting of representatives from Menlo Therapeutics Inc. and its designees will monitor safety data on a regular basis throughout the study.

4 SELECTION OF STUDY POPULATION

4.1 Study Population

Approximately 400 adult subjects with pruritus due to PN, AD, or psoriasis will be enrolled in this study.

4.2 Inclusion Criteria

Subjects must meet the following criteria to be enrolled into the study:

- 1. Male or female, age 18 years or older at consent.
- 2. Subject reports pruritus in the 24-hour period prior to enrollment and:
 - a. Has completed a prior applicable clinical study of seriopitant without an SAE that was assessed as likely related to the study drug

OR

- b. Has not participated in a prior clinical study of serlopitant and has a clinical diagnosis of PN, AD, or psoriasis, and Sponsor has approved enrollment.
- 3. All female subjects who are of childbearing potential must be willing to practice highly effective contraception (i.e., pregnancy prevention method with a failure rate of <1% per year, refer to section 7.1.5 for acceptable methods of contraception) from the time of the Baseline visit until 2 weeks after last dose of study drug.
- 4. Willing and able (has adequate cognitive ability, in the investigator's opinion) to comply with study visits and study related requirements including providing written informed consent.

4.3 Exclusion Criteria

Subjects who meet any of the following criteria are not eligible for participation in the study:

- 1. Presence of malignancy within 5 years prior to enrollment (exception for non-melanoma cutaneous malignancies).
- 2. Presence of a psychiatric diagnosis (such as major depressive disorder, bipolar disorder, schizophrenia, psychotic disorder, intellectual disability, severe alcohol abuse disorder) meeting Diagnostic and Statistical Manual of Mental Disorders, Fifth Edition criteria in past 3 years, history of suicidal ideation within the past 3 years or any history of suicidal attempt.
- 3. Presence of any medical condition or disability, that, in the investigator's opinion, could interfere with the assessment of safety in this study or compromise the safety of the subject.
- 4. Treatment with any investigational therapy within 4 weeks or 5-half-lives prior to enrollment (whichever is longer) or expected participation in another clinical study involving an investigational product or device during the subject's participation in MTI-107.
- 5. Treatment with other neurokinin-1 receptor (NK₁-R) antagonists (e.g., aprepitant, fosaprepitant, rolapitant) within 4 weeks prior to enrollment.
- 6. Treatment with strong cytochrome P450 3A4 inhibitors within 4 weeks prior to enrollment (Appendix B).
- 7. Currently pregnant or breastfeeding or planning to become pregnant during the study.

5 STUDY DRUG

5.1 Study Drug Supply, Route of Administration, and Storage

The study drug in this study is seriopitant 5 mg in a film-coated tablet formulation for oral administration. The seriopitant tablets contain microcrystalline cellulose, mannitol, croscarmellose sodium, silicon dioxide, sodium lauryl sulfate, and magnesium stearate, and are film coated with Opadry[®] Brown.

The study drug will be provided in bottles that can be stored at room temperature (59-86°F, 15-30°C).

Each bottle will each contain 18 serlopitant tablets.

Additional details regarding study drug supplies can be found in the Pharmacy Manual.

5.2 Labeling and Study Drug Accountability

The study drug will be appropriately packaged and labeled in bottles with 18 tablets per bottle. The study drug supplied for this study is not to be used for any purpose other than this study, and study drug accountability must be maintained for all bottles distributed to the investigative site.

Additional details regarding study drug labeling and accountability can be found in the Pharmacy Manual.

5.3 Dosing Regimen

During the treatment period, subjects will take one seriopitant 5 mg tablet once daily orally. Subjects will be instructed to take all doses from Baseline Visit (Study Day 1) until the Week 52 Visit, once a day and not within 2 hours before or after a meal.

Should the study drug be withheld (without intent to discontinue study drug, Section 5.6), the drug may be resumed at the discretion of the investigator, at the same dosing regimen.

5.4 Dose Modification

No dose modification of study drug will be allowed during this study.

5.5 Missed or Delayed Doses

Each dose of study drug after the first dose must be administered once daily, and not within 2 hours before or after a meal. If a dose is missed, that dose will be considered and documented as a missed dose. Dosing should resume as directed the next day.

5.6 Study Drug Discontinuation

Subjects should be discontinued from study drug in the following situations:

- Any medical condition that may jeopardize the subject's safety if study drug is continued, in the investigator's and/or Sponsor's opinion
- Baseline serum creatinine, total bilirubin, alanine aminotransferase (ALT) or aspartate aminotransferase (AST) > 2.5 times the upper limit of normal (ULN) (exception may be made for retesting within 28 days of enrollment as approved by the Medical Monitor)
- A female subject becomes pregnant
- The subject decides to discontinue study drug, or withdraws consent from the study
- The subject reports use of a strong CYP3A4 inhibitor (as listed in Appendix B) within 4 weeks of the study visit at which it was reported, initiates any investigational medication, or other NK₁-R antagonist (exception may be made for use of approved NK₁-R antagonist for less than 5 continuous days)

• Discontinuation is deemed to be in the best interest of the subject, in the investigator's and/or Sponsor's opinion

The Sponsor or designee should be contacted within 24 hours of investigator's awareness of any study drug discontinuation due to an AE or pregnancy. Investigators should make every effort to contact the Sponsor or designee before discontinuing study drug, if possible.

Subjects who discontinue study drug prior to completing the treatment period will enter a 4week follow-up period following the last dose of study drug (Section 6.4.10). Every effort should be made for subjects to complete this follow-up visit after a subject has discontinued from study drug.

5.7 Concomitant and Excluded Therapies

Concomitant therapies include any therapies (including over-the-counter medications) used by a subject from initiation of study drug through the follow-up period. A record of all medications used will be maintained for each subject throughout the study. Reported information will include a description of the type of drug, treatment period, dosing regimen, the route of administration, and drug indication. The use of any concomitant medication must relate to the subject's medical history or to an AE, except for vitamins/nutritional supplements and routine preventative immunizations.

5.7.1 Excluded Therapies

The following therapies and activities are excluded from the Baseline visit through the follow-up period:

- NK₁-R antagonists (other than study drug, exception may be made for use of approved NK₁-R antagonist for less than 5 continuous days)
- Strong CYP3A4 inhibitors (See Appendix B; exceptions may be made for use within 4 weeks of the study visit at which it was reported)
- Any investigational drug therapy other than seriopitant

Use of any excluded therapies should be reported as soon as possible, and will be recorded as protocol deviations for subjects who receive them. Subjects may be discontinued from the study drug (Section 5.6).

5.8 Assignment to Treatment

Eligible subjects will receive serlopitant 5 mg tablets.

5.9 Treatment Compliance

Records of study drug used, dosages administered, and intervals between visits will be kept during the study. Subjects will be asked to return all partially used and empty bottles to the study site at each visit. The site staff will count and record the number of remaining tablets in each returned bottle. Missed doses will be recorded as reported by the subject. A subject who has deviated significantly from the once-daily dosing regimen will be counseled.

6 STUDY SCHEDULE AND ASSESSMENTS

6.1 Efficacy Parameters

6.1.1 Itch Numeric Rating Scale

The Itch NRS is a validated, self-reported instrument for measurement of itch intensity. WI-NRS scores will be captured as per Appendix A. Subjects are asked to rate the intensity of their itch on an 11-point scale ranging from 0 (no itch) to 10 (worst itch imaginable). Higher scores indicate greater itch intensity. In this study, WI-NRS during a 24-hour recall period prior to the specified visit will be captured.

6.1.2 Investigator's Global Assessment of PN Stage

The IGA PN-S is an instrument used to assess the overall number and thickness of PN lesions at a given time point, as determined by the investigator. It consists of a 5-point scale ranging from 0 (clear) to 4 (severe). The IGA PN-S uses clinical characteristics including the number of nodules and their thickness, as guidelines for the overall severity assessment. IGA PN-S scores will be captured as per Appendix A. Each assessment during the study must be done by the principal investigator (PI) or designee. Every effort should be made to ensure that all assessments for a given subject are done by the same individual throughout the study. However, a change in assessor for a given subject, though not ideal, will not be considered a protocol deviation.

